8.4.1 Laboratory evaluations

The local hospital and/or clinic laboratory will be used for all laboratory evaluations required to determine eligibility. If eligibility laboratory assessments were not done during the patient's hospitalization, samples should be collected and sent to the local laboratory. A central laboratory will be used for analysis of all collected specimens from baseline through the final visit. Details on the collections, shipment of samples and reporting of results by the central laboratory will be provided to investigators in the laboratory manual. Results from the local hospital laboratory will be recorded in the eCRF.

Clinically notable laboratory findings are defined in [Appendix 1](#).

Local laboratory assessments may be performed on an as-needed basis for unscheduled visits. Laboratory values that exceed the boundaries of a notable laboratory abnormality must be commented on by the investigator on the source document and additional laboratory evaluations should be performed, as judged appropriate by the investigator. If the laboratory abnormality induces clinical signs or symptoms, or requires therapeutic intervention, then the diagnosis or medical condition must be entered on the patient's AE eCRF. If the laboratory abnormality is the primary reason for an unforeseen hospitalization or otherwise fulfills the seriousness category of an AE, then the procedure for rapid notification of SAEs must be followed. Likewise, if the laboratory abnormality leads to discontinuation from the study drug (temporarily or permanently), the patient must be followed until the abnormality resolves or until it is judged to be permanent. This investigation may include continued monitoring by repeat laboratory testing or by performing additional laboratory tests as deemed necessary by the investigator or the Novartis medical monitor.

Table 8-3 Laboratory Assessments

Test Category	Test Name
Hematology	Hemoglobin, hematocrit, red blood cell count, white blood cell count with differential (Basophils, Eosinophils, Lymphocytes, Monocytes, Neutrophils, Bands, Other (absolute value preferred , %s are acceptable), and platelet count will be measured at Visits 1 (local lab), 2, 7, 11, 13, 15, 16, and 17 (central lab). Hemoglobin A1c will be measured at Visits 2 and 17 (central lab).
Chemistry	Assessments required for eligibility that need to be measured at Visit 1 include creatinine, potassium, and total bilirubin. Blood urea nitrogen (BUN), glucose, creatinine, total bilirubin, AST (SGOT), ALT (SGPT), alkaline phosphatase, sodium, potassium, chloride, calcium , total protein, albumin, uric acid, and lipid profile be measured at Visits 1 (local lab), 2, 3, 5, 7, 9, 11, 13, 15, 16, and 17 (central lab).
Urinalysis	Dipstick-test determination of specific gravity, pH, blood, total protein, bilirubin, ketones, and leukocytes will be measured at Visit 2 (central lab). If dipstick is positive, a qualitative microscopic determination, including white blood cells high power field (WBCs/HPF) and red blood cells high power field (RBCs/HPF) will be performed.
Pregnancy Test	All female patients of childbearing potential will have a serum pregnancy test (hCG) performed at Visit 1 (local lab). In addition, these patients will have a urine pregnancy test conducted in the local laboratory at Visits 2, 5, 7, 11, 13, 15, 16 and 17. If any of these tests are positive at Visits 1 and 2, the patient should not be enrolled in the trial. If a patient should become pregnant during the trial, the patient may remain in the trial for follow-up visits but must discontinue study drug.

8.4.2 Electrocardiogram (ECG)

A standard 12 lead ECG will be performed at Visit 1. Interpretation of the tracing must be made by a qualified physician and documented on the ECG section of the CRF. Each ECG tracing should be labeled with the study, subject number and date and kept in the source documents at the study site.

Clinically significant abnormalities must be recorded on the CRF as either medical history and/or adverse events as appropriate.

8.4.3 Pregnancy and assessments of fertility

All pre-menopausal women who are not surgically sterile will have a serum pregnancy test (hCG) performed at Visit 1 (local lab). In addition, these patients will have a urine pregnancy test conducted in the local laboratory at Visits 2, 5, 7, 11, 13, 15, 16 and 17. . If any of these tests are positive at Visits 1 and 2, the patient should not be enrolled in the trial. If a patient should become pregnant during the trial, the patient may remain in the trial for follow-up visits but must discontinue study drug.

8.4.4 Appropriateness of safety measurements

The safety assessments selected are standard for the evaluation of patients with heart failure.

8.5 Additional assessments

Not applicable.

9 Study discontinuation and completion

9.1 Discontinuation

9.1.1 Discontinuation of study treatment

Discontinuation of study treatment for a patient occurs when study treatment is stopped earlier than the protocol planned duration, and can be initiated by either the patient or the investigator.

The investigator must discontinue study treatment for a given patient if he/she believes that continuation would negatively impact the patient's well-being.

Study treatment must be discontinued under the following circumstances:

- Patient/guardian decision
- Pregnancy
- Use of prohibited treatment as per recommendations in the prohibited treatment section
- Any situation in which study participation might result in a safety risk to the patient
- Following emergency unblinding
- Any severe suspected drug related AE at the investigator's discretion

- Suspected occurrence of angioedema. A patient with any signs or symptoms of clinically significant angioedema should be thoroughly evaluated by the investigator to determine if it constitutes a reason for discontinuation of study medication.
- Depending on the serum potassium, blood pressure, or eGFR, patient may need to have their study drug dose or the dose of another concomitant medication reduced or discontinued; or, if appropriate, have potentially contributing agents adjusted. Refer to appendices for treatment guidelines for hyperkalemia, hypotension or renal dysfunction, respectively.

If discontinuation of study treatment occurs, the investigator should make a reasonable effort to understand the primary reason for the patient's premature discontinuation of study treatment and record this information.

Patients who discontinue study treatment or who decide they do not wish to participate in the study further should NOT be considered withdrawn from the study UNLESS they withdraw their consent (see withdraw of informed consent section.). **Where possible, they should return for the assessments indicated** in the assessment schedule. If they fail to return for these assessments for unknown reasons, every effort (e.g. telephone, e-mail, letter) should be made to contact the patient/pre-designated contact as specified in the lost to follow-up section. This contact should preferably be done according to the study visit schedule.

If the patient cannot or is unwilling to attend any visit(s), the site staff should maintain regular telephone contact with the patient, or with a person pre-designated by the patient. This telephone contact should preferably be done according to the study visit schedule.

After study treatment discontinuation, at a minimum, in abbreviated visits, the following data should be collected at clinic visits or via telephone/email contact:

- new / concomitant treatments
- adverse events/Serious Adverse Events

The investigator must also contact the IRT to register the patient's discontinuation from study treatment.

If discontinuation occurs because treatment code has been broken, please refer to Emergency breaking of treatment code section.

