6.4 Dose modification

6.4.1 Dose modifications

For patients who do not tolerate the protocol-specified dosing schedule, dose interruptions and/or reductions are either recommended or mandated in order to allow patients to continue the study treatment.

Deviations to mandatory dose interruptions and/or reductions are not allowed. Permanent treatment discontinuation is mandatory for specific events listed in [Section 9.1.1](#).

These dose changes must be recorded on the appropriate case report form (CRF).

Every attempt should be made to maintain patients on the target study drug dose level for as long as possible throughout the study. If, however, in the opinion of the investigator, a patient is unable to tolerate the protocol-specified target dose, the investigator should consider whether dose adjustments of concomitant medications may rectify the situation before reducing the dose of study treatment. If adjustment of the concomitant medications is not possible or does not alleviate the side effects of concern, the investigator may down-titrate the dose of the study drug to the previous dose level. If needed, the study drug may be stopped completely, if this occurs, the patient should return to the clinic as soon as possible, after discontinuation of study drug, for an end of study visit. Patients may restart their current dose of study drug following an interruption of treatment, based on investigator judgment.

Study drug dose level adjustments should be mainly based on overall safety and tolerability with special focus on:

- Hyperkalemia
- Symptomatic hypotension
- Clinically significant decrease in eGFR/increase in serum creatinine (defined as a serum creatinine of $\geq 0.5\text{mg/dl}$ with at least a 25% decrease in eGFR)
- Angioedema

These changes must be recorded on the appropriate CRF. Every attempt should be made to titrate to and maintain patients on target study drug Dose Level 3 for as long as possible throughout the study. If, however, in the opinion of the investigator, a patient is unable to tolerate the protocol-specified target dose, the investigator will manage the patient's treatment according to the below guidelines:

Steps:

1. Adjust Concomitant Medications

- Dose adjustments/elimination of concomitant medications may remedy the situation before reducing the dose of study treatment. If adjustment of the concomitant medications is not possible or does not alleviate the side effects of concern, THEN;

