2. Adjust Study Treatment Dose Level

- Down-titrade study treatment to the previous dose level. The patient may continue receiving the lower dose level for a recommended period of 1 to a maximum of 4 weeks.
- A re-challenge to titrate back up to the target dose level should be attempted at 2 weeks, or when patient is deemed stable. THEN:

3. Further Adjust Study Treatment Dose Level

- If tolerability issues are not alleviated despite down-titration by one dose level, the investigator may down-titrade further to the next lower study treatment dose level. The patient may continue receiving the lower dose level for a recommended period of 1 to a maximum of 4 weeks. See Step 5.
- Again, once stable, the patient should be re-challenged with up-titration to the next higher dose level in an attempt to gradually bring the patient back to the target study treatment dose level (Dose Level 3).
- The investigator may choose the next dose level for down- or up-titration according to his or her clinical judgment.

4. Stopping Study Treatment

- If needed, the study treatment may be stopped completely, however, every effort must be made to complete an end of study visit and obtain follow up health status information and NT-proBNP for any patient that withdraws from the study.

5. Study drug restart after temporary treatment interruption

- Once the investigator considers the patient's condition appropriate for receiving the study drug, the investigator should re-start the patient on study treatment at the most appropriate and allowable dose level per his/her medical judgment.
- If tolerated, the patient should be titrated up to the next dose level every 1 to 4 weeks, as per the investigator's judgment.
- In some instances, Dose Level 1 or 2 could be maintained if the investigator considers that the patient's condition would not allow any further up-titration to the target dose of study medication (Dose Level 3). In this case, it would be acceptable to maintain the patient at Dose Level 1 or 2, whichever is the higher and tolerated dose level by the patient, but reasons for not getting to Dose Level 3 need to be captured in the eCRF.
- Should the patient not tolerate the re-start study drug dose level, he/she may be down-titrated again (if appropriate) or discontinued from study treatment.

Patients re-started on the study drug will retain their original randomization and study identification numbers.

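### Protocol 9.1.1 gives contradictory instructions on suspected angioedema and states no hold pending evaluation; 6.4.1 lists angioedema for dose adjustment without exempting it from re-challenge

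*Protocol*

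**What the plan says.** Protocol 9.1.1 opens its list with "Study treatment must be discontinued under the following circumstances". One of the eight bullets is "Suspected occurrence of angioedema". Its next sentence turns to patients with signs or symptoms of clinically significant angioedema and says that such a patient "should be thoroughly evaluated by the investigator to determine if it constitutes a reason for discontinuation of study medication". A separate bullet in the same list covers "Any situation in which study participation might result in a safety risk to the patient".

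Protocol 6.4.1 refers back to this list: "Permanent treatment discontinuation is mandatory for specific events listed in" Section 9.1.1. It does not say which events are meant. It then states: "Study drug dose level adjustments should be mainly based on overall safety and tolerability with special focus on" four items, namely hyperkalemia, symptomatic hypotension, a clinically significant fall in renal function, and angioedema. Five management steps follow. Step 2 (down-titration) says: "A re-challenge to titrate back up to the target dose level should be attempted at 2 weeks, or when patient is deemed stable". Step 3 covers further down-titration and renewed up-titration, Step 4 an optional complete stop, and Step 5 restart after a temporary interruption. A general sentence earlier in the section says: "Patients may restart their current dose of study drug following an interruption of treatment, based on investigator judgment".

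Protocol 6.4.2, the angioedema row of Table 8-2, and 10.2.1 define angioedema and set out the questionnaire, notification and serious adverse event duties.

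**The concern.** A stopping rule should tell a site what to do with the drug when the trigger occurs. Here the trigger is suspicion. The lead-in makes stopping compulsory, and the bullet then makes it a matter for the investigator's evaluation. Evaluating first is clinically reasonable, but the text does not say whether the patient keeps taking blinded tablets while that happens. One site could stop at once and another could keep dosing, and both could cite 9.1.1.

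The event is one the protocol takes seriously. Table 8-2 describes it as possibly dangerous, notes that severe cases can compromise the airway, and links it to enzyme inhibition that includes neprilysin. Section 5.2, criterion 9, excludes anyone with known prior angioedema of any cause. Naming it in 6.4.1 beside potassium, blood pressure and renal function suggests that a lower dose followed by re-challenge is an available response. Yet a patient who has had confirmed angioedema could not have been enrolled.

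What is at stake is patient safety and uniform conduct. The type I error rate and the sample size calculation do not depend on it.

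**Working it through.** No arithmetic applies beyond counting, so the check sets the relevant texts side by side.

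1. **The 9.1.1 bullet.** The lead-in is mandatory and the listed circumstance is suspicion. The second sentence narrows to clinically significant signs or symptoms and makes stopping the outcome of an evaluation. Two readings follow: (A) suspicion alone requires discontinuation; (B) the investigator evaluates and then decides. Reading B leaves dosing during the evaluation unaddressed.

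2. **Other angioedema text.** Section 6.4.2, Table 8-2 and 10.2.1 were read for any instruction on study drug. They require recognition, a questionnaire and reporting. None states an interruption pending evaluation.

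3. **The cross-reference from 6.4.1.** If its permanent-stop sentence meant every item in 9.1.1, reading A would prevail and restart would be barred. It cannot mean every item. Four of the 8 bullets are not unconditional permanent stops:
   - prohibited treatment, where 3 of the 5 rows of Table 6-3 provide for re-initiation;
   - severe suspected drug-related adverse events, left to the investigator's discretion;
   - angioedema, subject to evaluation;
   - potassium, blood pressure or eGFR, where the patient may need a reduction or a stop.

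   The other 8 − 4 = 4 (patient or guardian decision, pregnancy, safety risk, emergency unblinding) carry no such qualifier. Nothing says whether angioedema is one of the events meant, so the cross-reference leads back to the same ambiguous bullet.

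4. **The dose-adjustment list.** Of its 4 events, 3 have a management appendix (Appendices 2 to 4). Angioedema has its own sections, but they deal with recognition and reporting rather than dosing. Of the 5 steps in 6.4.1, 0 exempt angioedema.

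5. **How the protocol writes a clear rule.** For potassium of 6.0 mEq/L or more, Appendix 2 says to stop the drug at once, confirm, evaluate, and consider resuming at a lower dose below 5.5 mEq/L. For pregnancy, 6.4.1 tells the patient to stop immediately. Both state the first action without ambiguity. Angioedema has no equivalent. The pregnancy comparison concerns immediacy only, since that sentence does not expressly bar restart either.

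**The case against.** The strongest reply is that the list habitually uses bullets with their own qualifiers, so the second sentence is simply the operative condition and there is no contradiction. SAP 2.7.4.6, which records whether study medication was discontinued because of the event, fits that reading. This has force as to intent. It does not supply a rule for dosing during the evaluation, and it leaves suspicion standing under a mandatory heading.

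Second, suspicion is not left without any provision. It is itself on the must-stop list. The safety-risk bullet is worded widely enough to reach unconfirmed events, and 9.1.1 separately obliges the investigator to stop if continuing would harm the patient. A reader might infer that the protocol states no action on suspicion at all. The documents do not support that; the stated action is contradictory.

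Third, several provisions point against restart after a confirmed case. The glossary defines study treatment discontinuation as permanent. Step 5 and the general restart sentence concern interruptions. Section 6.6.2 ties re-challenge to systolic pressure, eGFR, potassium and the investigator's discretion. The safety-risk bullet would reasonably cover a confirmed event. A reader might therefore go too far in inferring that the protocol orders or endorses re-challenge after confirmed angioedema. It does neither; it fails to exclude it. The glossary is not decisive, because Table 6-3 and Appendix 2 both use discontinue for stops that may be followed by resumption. None of these provisions explains why angioedema is on the dose-adjustment list.

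Fourth, a reader might infer that suspected cases will be common, since 10.2.1 asks for wide vigilance about swelling in patients enrolled with fluid overload. The documents give no expected number, and the reporting trigger in 10.2.1 is broader than the clinically significant events in the evaluation sentence of 9.1.1.

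Finally, a Treatment Manual (6.1) and an angioedema manual (6.4.2) are mentioned but not available here. They may give sites a clear instruction, so divergence in practice is untested. The protocol text would still need correcting.

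**Conclusion.** The point holds as a minor patient-safety wording fault. The action on suspicion in 9.1.1 is contradictory, no hold pending evaluation is stated, and 6.4.1 lists angioedema for dose adjustment under steps with no exemption. The safeguards above limit the risk after a confirmed case, but they depend on each investigator giving them precedence over 6.4.1.

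The conclusion rests on the protocol and SAP text alone and assumes that no unseen manual is controlling. No patient count is claimed. Alpha and the planned power calculation are unaffected.

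**What to change.** In 9.1.1, replace the bullet with a rule along these lines: *Suspected angioedema: interrupt study drug pending evaluation; if confirmed, discontinue permanently with no re-challenge; if ruled out, study drug may be restarted under 6.4.1 Step 5; if unresolved, the investigator decides with the medical monitor.* An automatic permanent stop for every unresolved case is a debatable trade-off, which is why those cases are left to judgment.

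Delete angioedema from the 6.4.1 dose-adjustment list, or exempt it from Steps 2, 3 and 5. Add a cross-reference from 6.4.2 to the 9.1.1 rule.

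The cost is one sentence, one deletion and one cross-reference, carried by an amendment under 14.1 and a letter to sites. The questionnaire already captures discontinuation due to the event, so no new data are needed.

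The downside is that some patients whose swelling is later ruled out will pause drug briefly. Patients who stop stay in follow-up under 9.1.1, and the SAP's treatment-policy strategy (2.5.2) is meant to keep them in the comparison, but inclusion is not automatic. The minimum data after stopping are treatments and adverse events, possibly by telephone or email. Section 6.4.1 sends patients who stop completely to an end-of-study visit. Section 12.4.2 excludes anyone without a baseline value or without both the Week 4 and Week 8 values. The site letter should therefore ask for Week 4 and Week 8 NT-proBNP samples regardless of treatment status.

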9.1.2 Withdrawal of informed consent

Patients may voluntarily withdraw consent to participate in the study for any reason at any time. Withdrawal of consent occurs only when a patient:

- Does not want to participate in the study anymore, and
- Does not allow further collection of personal data

Every effort should be made to encourage trial continuation to collect information regarding the secondary clinical endpoints (CV Death, HF Hospitalization, and Urgent HF Visits) during the longer term follow-up (Amendment 1 and subsequent versions).

In the situation the patient still wants to withdraw, the investigator should make a reasonable effort (e.g. telephone, e-mail, letter) to understand the primary reason for the patient's decision to withdraw his/her consent and record this information.

Study treatment must be discontinued and no further assessments conducted, and the data that would have been collected at subsequent visits will be considered missing.

Further attempts to contact the patient are not allowed unless safety findings require communicating or follow-up.

All efforts should be made to complete the assessments prior to study withdrawal. A final evaluation at the time of the patient's study withdrawal should be made as detailed in the assessment table.

Novartis will continue to keep and use collected study information (including any data resulting from the analysis of a patient's samples until the time of withdrawal) according to applicable law.

For US: All biological samples not yet analyzed at the time of withdrawal may still be used for further testing/analysis in accordance with the terms of this protocol and of the informed consent form.

